A Phase I/II Study of Decitabine in Combination with Sequential Rapamycin or Ribavirin in High Risk AML Patients

ULEU-13049

Clinical trials.gov # NCT02109744

Principal Investigators

[name].

[name]

Co-Investigators
[name].
[name].
[name].
[name]., Ph.D.

Statistician: [name].

SYNOPSIS:

OBJECTIVES:

- 1.1 To determine the efficacy of decitabine followed by rapamycin in previously untreated elderly patients not able to receive standard chemotherapy or in patients with relapsed or refractory AML, through measurement of CR, CRp, PR, and event free and overall survival (ArmA).
- 1.2 To determine the safety of administration of decitabine with escalating doses of ribavirin in elderly leukemia patients or patients with relapsed/refractory disease with M4/M5 subtypes anticipated to express high eIF4E at diagnosis (ArmB).
- 1.3 To establish effect of these sequential treatments on expression of PI3K/Akt /mTOR pathway proteins and on eIF4E activation through Western blot and phospho-flow methodologies.
- 1.4 To correlate the clinical response with baseline expression of phospho-p70S6K/pAKT and with the in vitro inhibitory effects of mTOR inhibition with rapamycin or ribavirin on the level of downstream effectors
- 1.5 To determine whether a leukemia stem cell phenotype is inhibited by the sequential administration of decitabine/rapamycin or decitabine/ribavirin.

TARGET POPULATION: Elderly (>65 years old) AML patients who are not otherwise candidates for standard induction chemotherapy or who refuse such therapy OR adults with relapsed or refractory AML. AML may have relapsed after any number of remissions or after stem cell transplantation in the absence of clinically significant GVHD. For inclusion/exclusion criteria, see 3.1 and 3.2.

RATIONALE: Decitabine, a demethylating agent, has been found to have activity in elderly patients with AML and in patients with high risk MDS. mTOR inhibitors such as rapamycin have been found to be inhibitory to AML stem cells and to have activity in some patients with AML. By combining agents, which have been shown to have potential for additive or synergistic effects in vitro, the response rate and safety in relapsed/refractory patients will be determined. In our phase I study, it was found that a daily dose of 2 mg Rapamycin resulted in therapeutic levels and was safely administered.

Rapamycin does not always effectively inhibit protein translation in AML due to inability to inhibit 4E-BP-1. There is data that ribavirin, an agent which inhibits methyl 7G cap translation via inhibition of eIF4E can suppress AML growth in those cases with high baseline expression or aberrant nuclear localization of eIF4E. In those M4/M5 AML cases known to express high eIF4E expression, we will therefore examine ribavirin effects in conjunction with decitabine as it is anticipated that rapamycin would be less effective in these cases.

DURATION OF STUDY: Number of cycles will be determined based on response with maximum of 6 cycles to be given. See 4.1.1.

ULEU-13049 2 Version date: 09Aug2017

[figure not shown]
STUDY DESIGN: Open label single arm phase II design in arm A and standard dose escalation design in Arm B. In arm A, Decitabine will be given at 20 mg/m² for 10 days in cycle 1 followed by rapamycin orally on days 11 to 22 at 2 mg/day after a 6 mg loading dose on day 11. In subsequent cycles, decitabine will be given for 5 days. This arm of the study will be conducted using a Simon two stage model to maximize efficacy and minimize toxicity.

In arm B, in those with high eIF4E (FAB subtypes M4/M5), after completion of the 10 days of decitabine, ribavirin will be administered at either 1000 mg bid, 1200 mg bid, or 1400 mg bid on days 11 through 28. In cycles beyond the first, ribavirin will be given from days 1 through 28, and decitabine will be given for 5 days.

CORRELATIVE STUDIES: Endpoints of mTOR inhibition and protein translation inhibition will be measured at various time points during the study. We will also assay for inhibition of a leukemia initiating stem cell phenotype and functionality at defined time points during the trial.

ULEU-13049 3 *Version date: 09Aug2017*

STUDY SCHEMA

Outline

- 1.0 Study Objectives
- 2.0 Background
 - 2.1 Relapsed and refractory AML/ AML in elderly
 - 2.2 Decitabine
 - 2.3 mTOR pathway and leukemia
 - 2.4 Rapamycin
 - 2.5 Ribavirin
 - 2.6 Rationale for the combination of decitabine and an mTOR inhibitor
 - 2.7 Rational for combination of decitabine and ribavirin
- 3.0 Patient Selection
 - 3.1 Eligibility criteria
 - 3.2 Exclusion criteria
 - 3.3 Inclusion of women and minorities
 - 3.4 Study duration and dates
 - 3.5 Prior and concomitant medications
- 4.0 Treatment Plan
 - 4.1 Agent administration
 - 4.1.1 Study schema
 - 4.1.1.1 Monitoring
 - 4.1.2 Informed Consent
 - 4.1.3 Registration

Appendix 1 Performance status criteria

Appendix 2 Cockcroft-Gault Equation

Appendix 3 Common Terminology Criteria for Adverse Events (CTCAE)

Appendix 4 Declaration of Helsinki

Appendix 5 Study Calendar

1.0 OBJECTIVES

- 1.1 To determine the efficacy of decitabine followed by rapamycin in previously untreated elderly patients not able to receive standard chemotherapy or in patients with relapsed or refractory AML through measurement of CR, CRp, PR, and event free and overall survival.
- 1.2 To determine the safety and feasibility of the combination of decitabine given at a fixed dose with sequential rapamycin in previously untreated elderly patients not able to receive standard chemotherapy or in patients with relapsed or refractory acute myeloid leukemia with M4/M5 subtypes known to express phosphorylated eIF4E at diagnosis.
- 1.3 To establish effect of this sequential treatment on expression of PI3K/Akt /mTOR pathway proteins through Western blot and phospho-flow methodologies. In those receiving ribavirin, effect on levels of phospho-eIF4E expression will be measured as will effects on protein translation.
- 1.4 To correlate the clinical response to sequential decitabine with rapamycin or ribavirin with baseline expression of phospho-p70S6K/pAKT.
- 1.5 To determine leukemia stem cell frequency in the setting of AML relapse and in de novo elderly AML patients and to determine if that frequency is decreased after decitabine alone or after decitabine followed by rapamycin or ribavirin.

2.0 BACKGROUND

2.1 Relapsed and refractory AML and AML in the 65 years and older population

Acute myeloid leukemia (AML) is a clonal hematopoietic disorder whereby normal progenitor cells no longer differentiate normally or respond to regulators of proliferation, resulting in the accumulation of leukemic blasts in the blood, bone marrow and other tissues. There are an estimated 14,000 new cases of AML diagnosed in the United States each year with a median age at diagnosis of 69. Standard initial treatment has generally consisted of the combination of an anthracycline, such as daunarubicin or idarubicin, and cytarabine with complete remission rates in patients aged 18-60 years approaching 65% to 75%. In older patients, the complete remission rates are lower, between 40% and 60%, with a probability of survival at 2 years between 19% and 25%. Therefore, there remains a population of patients that will either not achieve a remission after initial induction therapy or will relapse soon thereafter and require salvage therapy. Regardless, complete remission rates and overall survival after relapse tend to be poor.

When possible, relapsed patients are offered high-dose chemotherapy or reduced intensity therapy with hematopoietic stem cell transplant (HSCT), which is the only therapy associated with a reasonable chance of durable remission after relapse. However, the majority of relapsed patients will be ineligible for HSCT either because of a lack of

ULEU-13049 7 *Version date: 09Aug2017*

donor, advanced age, or the presence of other medical co-morbidities that would increase the potential morbidity of the procedure. As a result, therapeutic options available to date remain unsatisfactory for the majority of patients with relapsed AML. Also, relapse after allogeneic stem cell transplantation is usually compatible with a survival of only weeks. Novel therapies should be investigated for the potential to improve remission duration and length of survival while at the same time limiting toxicity in this population of patients.

Because elderly patients often have a lower response rate to standard chemotherapy regimens and have a higher rate of mortality during such treatments, especially when diagnosed at age >70 years, other therapies are now utilized in this patient group such as hypomethylating agents, clofarabine, and other investigational approaches. It is generally held that there is no standard of care for induction therapy in elderly AML patients ^{2,3}.

2.2 Decitabine

2.2.1 Effects in Humans

Decitabine is a unique agent with a dual mechanism of anticancer action. Although the compound was first synthesized over 40 years ago, only recently has the dual mechanism of action been elucidated. High doses of decitabine are cytotoxic while lower doses are associated with DNA hypomethylating activity. This information sparked clinical trials using lower doses since in the original studies higher doses were associated with dose-limiting myelosuppression. Studies using such lower dosing schedules, particularly in patients with hematologic malignancies, have shown significant promise for the future use of demethylating agents. In May of 2006 the United States Food and Drug Administration approved the use of decitabine (DACOGEN for Injection) for the treatment of MDS. The current focus for the clinical use of decitabine is for the treatment of hematologic malignancies, namely MDS as well as AML, as a single agent or in combination with other agents.

2.2.2 Rationale for the Use of Decitabine in Hematologic Malignancies

Reports suggest frequent methylation of the p15^{INK4B} gene promoter in leukemias, and it has been proposed that this methylation could be necessary for leukemic cells to escape inhibitory signals from the bone marrow environment by silencing p15 expression.^{4,5} p15^{INK4B} is a regulator of the G1/S phase cell cycle transition which negatively regulates cell-cycle dependent kinases, the activity of which is necessary to activate the Retinoblastoma protein transcription factor.⁶ Furthermore, several studies report increased p15 gene methylation in MDS patients, and this methylation pattern appears to become more apparent with MDS disease progression.^{7,8} An agent such as decitabine or 5-azacytidine, with documented activity of hypomethylation of DNA would then be expected to affect the natural history of MDS and leukemias and demonstrate clinical activity.

ULEU-13049 8 Version date: 09Aug2017

Correlative investigations of Daskalakis et al. explored decitabine-induced p15 gene demethylation in bone marrow mononuclear cells collected before and during treatment with decitabine. Samples were collected from 23 intermediate /high risk MDS subjects enrolled in a decitabine Phase 2 study. In these samples, p15 gene hypermethylation (defined as >15% methylation) was observed in 15 of 23 patients at baseline (median, 29%; range, 16-54%). Hypermethylation occurred in all FAB subtypes and thus was not limited to the presence of excess bone marrow blasts. Of the 23 subjects that received one or more courses of low-dose decitabine, 19 were evaluable for changes in p15 gene methylation. Of the 12 subjects with p15 hypermethylation prior to decitabine treatment, 9 responded to treatment with at least a 25% decrease (median, 16%; range, 5 to 34%). One subject had a <25% decrease, and in 2 subjects, p15 methylation increased. Subjects without initial p15 hypermethylation showed no changes in methylation during continued treatment. In 10 subjects, p15 immunohistochemical staining was performed on serial biopsies, and in 4 of 8 cases with p15 gene hypermethylation, cytoplasmic p15 expression was very low or absent prior to treatment while in the other 4 subjects and the 2 subjects without hypermethylation, cytoplasmic p15 levels were comparable to normal bone marrow. Following 1 to 3 courses of decitabine, p15 expression was induced to high levels in all 4 subjects with initially low or absent expression. This was paralleled by hypomethylation. The study concluded that emergence of partially demethylated epigenotypes and re-establishment of normal p15 protein expression following decitabine treatment implicate pharmacologic demethylation as a possible mechanism of response in MDS. Other studies have documented global hypomethylation with decitabine but have not been able to associate responses with increased expression of a given gene. 10

2.2.3. Clinical Experience with Decitabine in AML and MDS

Treatment of patients with myelodysplastic syndromes (MDS) with decitabine leads to transfusion independence and a longer median time to progression to AML or death as compared to patients treated with supportive care only¹¹. In vitro data have shown that decitabine is able to induce terminal differentiation of leukemic blasts, which acquire the morphological and cytologic characteristics of fully differentiated monocytes and macrophages. Additionally, treated cells regained their innate functional ability. Decitabine has also been shown to have activity in MDS patients with intermediate or high risk International Prognostic Scoring System (IPSS) scores. 34% of patients had normalization of bone marrow and peripheral counts. A dosing scheme using 20 mg/m² daily intravenously for 5 days has been found to be as efficacious as other more complicated dosing schedules¹². Subsequent studies have shown activity as a first-line treatment in all cytogenetic subgroups of older AML patients¹³. Furthermore, decitabine has been successfully and safely combined with histone deacetylase inhibitors (HDACs) such as valproic acid, suberoylanilide hydroxamic acid (SAHA) and vorinostat as well as with standard chemotherapy regimens. 14 Recently, decitabine has been utilized in elderly patients with AML

with some success¹⁵as upfront therapy and response rates up to 40% have been noted with ten day courses in a similar dosing scheme ¹⁶.

2.3 mTOR Pathway and Leukemia

The mammalian target of rapamycin (mTOR) is a serine/threonine kinase involved in the regulation of synthesis of proteins involved in cell cycle progression¹⁷. It appears to be a nutrient sensing protein with dual regulation by amino acid availability as well as mitogen activation by the upstream PI3K/AKT pathways.¹⁷ The eukaryotic initiation factor 4 E (eIF4E), which is downstream from mTOR, is necessary for recruitment of the ribosome to mRNA, the rate limiting step in protein translation. The formation of the eIF4E complex is regulated by 4E-BP1 and in the unphosphorylated form it binds to eIF4E and inhibits its activity and protein translation is halted, while when 4E-BP1 is phosphorylated, there is decreased affinity for eIF4E and translation can occur. A separate downstream target of mTOR, p70S6K, is also involved in protein translation. When activated by mTOR, it is able to phosphorylate the 40S ribosomal protein S6 that then allows translation to occur.¹⁸

Constitutive activation of PI3K/AKT/mTOR signaling has been shown in leukemic blasts with 50-70% of patients displaying phosphorylated AKT.¹⁹ There are multiple possible mechanisms for this activation which include activating Ras or c-KIT mutations, upregulation of PI3K p110δ, autocrine/paractine VEGF secretion and others.¹⁹ There also appears to be an upregulation of this pathway not only in the bulk AML population, but also in leukemia stem cells transplanted in NOD/SCID mice models.²⁰ Activation of this pathway results in disrupted control of proliferation resulting in a competitive growth advantage for the leukemic cells. Inhibitors of the mTOR pathway either alone or in combination may block the activated signaling cascade or lead to inhibition of tumor growth and apoptosis.²⁰

2.4 Rapamycin

Rapamycin is a macrolide fungicide isolated from the bacteria Streptomyces hygroscopicus with potent antimicrobial, immunosuppressant and antitumor activities and is approved for the prevention of allograft rejection following organ transplantation. Rapamycin binds to the immunophilin FK506 binding protein 12 (FKBP12) and forms a complex which then binds to mTOR and inhibits downstream signaling events. The sensitivity of various AML cell lines to increasing concentrations of rapamycin in clonogenic assays has been measured. There appears to be a variable degree of sensitivity with UT-7EPO and UT-7GM cell lines being insensitive, K562, U937, HEL and HL60 being moderately sensitive and the immature KG1 and KG1a cell lines being strongly inhibited by low concentrations of rapamycin. Nine patients with relapsed, refractory or poor-risk AML were treated with rapamycin as a single agent, with a partial response (> 50% reduction in the absolute number of blasts or at least a 50% reduction in the percentage of marrow blasts) occurring in 4 patients. 4 patients had progressive disease and one had stable disease. ²² As a single agent, rapamycin has had minimal activity in AML. Rapamycin has been combined with cytototoxic chemotherapy in newly

ULEU-13049 10 Version date: 09Aug2017

diagnosed patients in early phase trials²³ with no positive effects on CR rates noted. Rapamycin has also been utilized in the therapy of ALL, and it is also used after allogeneic stem cell transplantation for prophylaxis of graft vs. host disease in combination with tacrolimus or methotrexate.

2.5 Ribavirin

One of the reasons postulated for limited impact of mTOR inhibitors in AML is that first generation inhibitors such as rapamycin do not inhibit the mTORC2 component of mTOR and they also fail to inhibit 4E-PB1 phosphoryaltion, thereby allowing translation initiation to occur. Unlike rapamycin, ribavirin is a competitive inhibitor of the cap moiety, thereby inhibiting the mRNA export and translation function of eiF4E. eIF4E activity has been found to be most elevated in M4 and M5 AML (44/44 cases), and there is accumulation of nuclear bodies and less eiF4E in the cytoplasm when overexpression occurs. When used as a single agent in 11 M4 and M5 AML cases, there was 1 CR, 2 PRs, 2 blast responses, 4 stable disease, and 2 progressive disease outcomes ²⁴

2.6 Rationale for the Combination of Decitabine and an mTOR Inhibitor

Decitabine has shown efficacy in the treatment of patients with myelodysplastic syndrome as well as AML. Rapamycin has also been shown to have activity in patients with AML. The combination of decitabine with rapamycin will allow us to test the potential beneficial effect of targeting two separate pathways that appear aberrant in this disease. Since successful maintenance dose escalation studies with a demethylation agent have been reported after cytotoxic chemotherapy as well as after stem cell transplantation and since rapamycin has effective GVHD activity without adversely impacting donor chimerism, we also wish to test the combination of decitabine and rapamycin in patients who relapse after allografting.²⁵ It is also anticipated that this combination may be synergistic in that rapamycin by itself may activate pAKT via mTORC2 and IGFR1 mechanisms. ¹⁹

In order to test the rationale for combining a demethylating agent with an mTOR inhibitor preclinically, AML cell lines were exposed to 5-azacytidine at 1 to 16 uM, with the IC50 determined to be 4-8 uM. 5-azacytidine increased apoptosis above control whereas rapamycin by itself had minimal effect on apoptosis as assessed in an Annexin V flow cytometric assay. Effects on proliferation at concentrations of Rapamycin up to 100 nM were also minimal. In the U937 cell line, the combination index was 0.465 (10 μM 5-azacytidine and 100 nM rapamycin), indicating synergism. For MV411, the combination index was 0.736, and for KG1a, 0.118, also indicating synergism. For HL60, no synergism was noted. Exposure to the combination of 5-azacytidine and rapamycin resulted in greater suppression of AKT and 4EBP1 phosphorylation than did either agent singly. Four days of AML cell line exposure to decitabine followed by 100 nM Rapamycin also results in inhibition of cell proliferation. This in vitro data (published only in abstract form to date²⁶) utilizing a demethylating agent and an mTOR inhibitor lends support to rational combination of this regimen in vitro.

ULEU-13049 11 Version date: 09Aug2017

2.7 Rationale for combination of decitabine and ribavirin

As noted above, while mTOR inhibitors are not always effective in inhibiting translation in AML, ribavirin has that potential in cases where eIF4E is activated and expressed. In this trial, we will therefore examine the use of ribavirin in dose escalation fashion built on a 10 day decitabine backbone in those M4/M5 subtype patients who express high eIF4E levels.

3.0 PATIENT SELECTION

3.1 Inclusion Criteria

- $3.1.1 \text{ Age} \ge 18$
- 3.1.2 Diagnosis of AML according to WHO (World Health Organization) criteria except acute promyelocytic leukemia AND
- 3.1.3 Refractory AML defined as failure to achieve CR after 2 cycles of induction chemotherapy or persistence of > 40% bone marrow blasts after one cycle of chemotherapy induction $\underline{\mathbf{OR}}$
- 3.1.4 Relapsed AML defined as any evidence of disease recurrence after achieving a documented first or greater CR $\overline{\mathbf{OR}}$
- 3.1.5 Relapsed AML after stem cell transplantation. 90 days (since stem cell infusion) must have elapsed between transplant and emergence of recurrent AML**OR**
- 3.1.6 Newly diagnosed AML in a patient >65 years old not considered fit for standard 7+ 3 chemotherapy or who declines such therapy after discussion of therapeutic options available.

3.1.7 ECOG performance status <3 (Appendix 1)

3.2 Exclusion Criteria

- 3.2.1 Abnormal renal function as evidenced by a calculated creatinine clearance ≤ 30 ml/min (Cockcroft-Gault formula (Appendix 2)
- 32.2 Abnormal liver function: Bilirubin >2.0 mg/dl, transaminase(s) more than
- 2.5x the upper limits of normal
- 3.2.3 Active systemic infection not responding to antibiotics
- 3.2.4 Known diagnosis of human immunodeficiency virus infection (HIV)
- 3.2.5 Patients who are post-allogeneic transplantation should not have active GVHD greater than grade 1 of skin at time of enrollment. They may have had DLI but not within 4 weeks of beginning the study.
- 3.2.6 Pregnant or breast feeding female subjects
- 3.2.7 Known or suspected CNS leukemia involvement; past involvement is not an exclusion.

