4.4 Dose Calculation

Dose of decitabine will be based on body surface area calculated on actual body weight. No correction for obesity will be made. The dose of rapamycin or ribavirin is a fixed, non-calculated dose.

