5.3.2 CLINICAL PHARMACOLOGY

Mechanism of Action

• Ribavirin is an antiviral drug

Pharmacokinetics

- Multiple dose ribavirin pharmacokinetic data are available for HCV patients who received ribavirin in combination with peginterferon alfa-2a. Following administration of 1200 mg/day with food for 12 weeks mean±SD (n=39; body weight greater than 75 kg) AUC0-12hr was 25,361±7110 ng·hr/mL and Cmax was 2748±818 ng/mL. The average time to reach Cmax was 2 hours.
- The terminal half-life of ribavirin following administration of a single oral dose of is about 120 to 170 hours. The total apparent clearance following administration of a single oral dose of is about 26 L/h. There is extensive accumulation of

ULEU-13049 25 Version date: 09Aug2017

ribavirin after multiple dosing (twice daily) such that the Cmax at steady state was four-fold higher than that of a single dose.

Effect of Food on Absorption of Ribavirin

- Bioavailability of a single oral dose of ribavirin was increased by coadministration with a high-fat meal.
- Elimination and Metabolism
- The contribution of renal and hepatic pathways to ribavirin elimination after administration of is not known. In vitro studies indicate that ribavirin is not a substrate of CYP450 enzymes.
- Renal Impairment
- A clinical trial evaluated 50 subjects with either moderate (creatinine clearance 30 to 50 mL/min) or severe (creatinine clearance less than 30 mL/min) renal impairment or end stage renal disease (ESRD) requiring chronic hemodialysis (HD). The apparent clearance of ribavirin was reduced in subjects with creatinine clearance less than or equal to 50 mL/min, including subjects with ESRD on HD, exhibiting approximately 30% of the value found in subjects with normal renal function. Pharmacokinetic modeling and simulation indicates that a dose of 200 mg daily in patients with severe renal impairment and a dose of 200 mg daily alternating with 400 mg the following day in patients with moderate renal impairment will provide plasma ribavirin exposures similar to that observed in patients with normal renal function receiving the standard 1000/1200 mg daily dose. These doses have not been studied in patients.

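### Arm B admits patients with creatinine clearance of 31–50 mL/min at the full fixed ribavirin dose, although section 5.3.2 puts their ribavirin clearance at about 30% of normal

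*Combined protocol and SAP*

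**What the plan says.** - **Eligibility.** Section 3.2.1 excludes "Abnormal renal function as evidenced by a calculated creatinine clearance ≤ 30 ml/min", by Cockcroft-Gault (Appendix 2). Arm B has no separate limit.
- **Dose.** Section 4.4: "The dose of rapamycin or ribavirin is a fixed, non-calculated dose". Section 4.1.1 starts Arm B at 1000 mg bid (2000 mg/day), with Level 3 at 1400 mg bid (2800 mg/day) and the lowest level, -2, at 600 mg bid (1200 mg/day). Ribavirin runs from day 11 to day 28 in cycle 1 and continuously from cycle 2.
- **Pharmacology.** Section 5.3.2: "The apparent clearance of ribavirin was reduced in subjects with creatinine clearance less than or equal to 50 mL/min", "exhibiting approximately 30% of the value found in subjects with normal renal function". That figure pools moderate impairment (30–50 mL/min), severe impairment and dialysis. For moderate impairment the section models "a dose of 200 mg daily alternating with 400 mg the following day in patients with moderate renal impairment" as giving exposure similar to 1000/1200 mg/day in normal function, and adds: "These doses have not been studied in patients".
- **Reductions.** Section 4.5.3.2 holds ribavirin for non-hematologic toxicity, steps it down as far as 600 mg bid, then stops it. Section 4.5.3.1 makes no change for hematologic toxicity. Section 4.5.4 leaves other changes to the treating physician. None of these ties a ribavirin dose to renal function.

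**The concern.** The protocol reproduces a renal warning for ribavirin but does not carry it into eligibility or dosing. The 30 mL/min cut-off removes severe impairment and leaves in the moderate band, for which section 5.3.2 models a much lower dose.

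What is at stake is patient safety. An identifiable group would start at an exposure well above the one intended for its dose level, and the written response begins only once toxicity has appeared. The group is foreseeable: the trial takes patients over 65 who are unfit for standard induction. By the Appendix 2 formula, a 78-year-old of 70 kg with creatinine 1.3 mg/dL has (140 − 78) × 70 / (1.3 × 72) = 46 mL/min and is eligible.

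**Working it through.** **Step 1. Reproduce the modelled dose in section 5.3.2.** The mean of 200 and 400 mg is 300 mg/day. At steady state with linear kinetics, exposure = dose / clearance, so matching dose = f × reference dose, where f is clearance relative to normal. With f = 0.30, 0.30 × 1000 = 300 mg/day, which agrees exactly. Against 1200 mg/day, the implied f is 300/1200 = 0.25. The modelled dose for moderate impairment thus implies f of 0.25–0.30, close to the pooled 30%.

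**Step 2. Apply this to Level 1 (2000 mg/day).** Exposure ratio = 1/f. Dose matching Level 1 in normal function = 2000 × f. The last column divides the lowest planned level (1200 mg/day) by that dose. The values 0.40 and 0.50 are assumptions, included because 30% is a pooled figure.

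| f | Exposure ratio | Dose matching Level 1 | 1200 mg/day over match |
|---|---|---|---|
| 0.25 | 4.0 | 500 mg/day | 2.4 |
| 0.30 | 3.3 | 600 mg/day | 2.0 |
| 0.40 | 2.5 | 800 mg/day | 1.5 |
| 0.50 | 2.0 | 1000 mg/day | 1.2 |

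Level 1 to Level 3 spans 2800/2000 = 1.4. At steady state, Level 1 in such a patient acts like 2000/0.30 = 6,667 mg/day, or 2.4 times Level 3. At f = 0.50 it acts like 4,000 mg/day, or 1.4 times Level 3.

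**Step 3. How quickly this is reached.** Section 5.3.2 supports two half-lives. One is the single-dose terminal value: "The terminal half-life of ribavirin following administration of a single oral dose of is about 120 to 170 hours". The other follows from its statement that "the Cmax at steady state was four-fold higher than that of a single dose". For 12-hourly dosing, accumulation = 1/(1 − exp(−12k)); setting this to 4 gives k = −ln(0.75)/12, a half-life of 28.9 h. (The terminal values would give accumulation of 14.9 to 20.9.)

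Assume constant-rate input, unchanged volume and impaired rate constant f × k. Then AUC to time T is proportional to T/k − (1 − exp(−kT))/k². Cycle 1 has 18 ribavirin days (T = 432 h); cycle 3 is the third 28-day cycle, with continuous dosing. Ratios to normal function:

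| f | Cycle 1: 28.9 / 120 / 170 h | Cycle 3: 28.9 / 120 / 170 h |
|---|---|---|
| 0.30 | 2.56 / 1.56 / 1.40 | 3.33 / 3.04 / 2.75 |
| 0.50 | 1.79 / 1.36 / 1.27 | 2.00 / 1.96 / 1.89 |

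The cycle 1 excess is smaller than the steady-state figure and depends on the half-life. By cycle 3 it is near the steady-state value on every assumption.

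**The case against.** **The evidence is indirect.** The 30% is pooled, section 5.3.2 says the renal and hepatic shares of elimination are unknown, and the reduced doses are only modelled. Section 4.1.1 says the trial's doses were tolerated in earlier studies. All of this stands. But the modelled dose specific to moderate impairment implies the same reduction, and exposure still doubles at an assumed 50%. The documents do not show the renal criteria of the earlier studies.

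**Safeguards exist.** Renal chemistry is checked twice weekly, ribavirin can be held, reduced and finally stopped, and section 4.5.4 gives the physician discretion. These limit harm once it shows. They do not set the starting dose.

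**Frequency is unknown.** The example patient is at the top of the age range of the earlier phase I study (section 2.6). At the same weight and creatinine, age 69 gives 53 mL/min and age 63 gives 58, both above the band. The documents give no prevalence. This limits the weight of the point, not its direction.

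Four stronger readings are tempting, and the documents do not support them:

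- *Level 1 is 6.7 times, and even 600 mg bid four times, the matching dose.* That compares with 300 mg/day, which matches 1000/1200 mg/day. Against this trial's 2000 mg/day the match is 500–600 mg/day.
- *The 30-day cohort review would miss the excess.* Section 4.1.1 sets 30 days as a minimum for the last patient enrolled. At two accruals a month (section 3.4), all assumed to be in Arm B, the first two of three patients would be near days 60 and 45. On the model above with f = 0.30, they would already have 48–64% and 23–41% of the three-cycle excess AUC.
- *The MTD would be biased.* There is no prevalence or exposure-toxicity relation from which to derive this. DLTs are non-hematologic only (section 9.4), and one DLT in three only expands the cohort.
- *Unmodified hemolytic anemia is the main danger.* Section 5.3.3.2 calls it the primary toxicity but says it has not been a problem in AML trials so far. Blood counts are twice weekly and transfusion thresholds are set.

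**Conclusion.** The point holds as a safety gap in eligibility and starting dose and should be fixed. As written, an Arm B patient at 31–50 mL/min receives a starting dose that gives about 3.3 times normal-function exposure at steady state, or 2.0 times at 50% clearance. The lowest planned level remains 2.0 to 2.4 times the dose matching Level 1 at the clearance section 5.3.2 implies (1.2 times at 50%).

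This rests on linear kinetics and on applying the section 5.3.2 figures to this population. Confidence is medium because the number of such patients, and the toxicity the extra exposure would cause, cannot be taken from the documents.

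**What to change.** Change section 3.2.1 to exclude calculated creatinine clearance ≤30 mL/min in Arm A or ≤50 mL/min in Arm B. Exclusion is preferred to a scaled dose because the reduced doses are unstudied in patients.

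It costs one eligibility line and no new measurement, since the clearance is already calculated at entry. The downsides are real. M4/M5 patients at 31–50 mL/min could not enter the trial at all, because arm is set by FAB subtype alone and Arm A is closed to them. Arm B accrual would slow by an unknown amount, and the MTD would apply only above 50 mL/min. The change also does not cover a patient whose clearance falls below 50 mL/min during treatment; that would still rest on section 4.5.4.
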